4.2 CORRELATIVE STUDIES

Please see the lab manual for further details of these analyses.

Apoptosis

Cleaved Caspase-3. Caspase-3 is a central downstream executor of both the intrinsic and extrinsic apoptosis pathways, and is responsible for the proteolytic cleavage of key effector molecules such as nuclear poly (ADP-ribose) polymerase (PARP).²⁹ Cleavage of the zymogen form of caspase-3 to its active p17 and p12 fragments by caspase 8,9,10, or 12 is essential for downstream induction of apoptosis. The primary endpoint is comparison of apoptosis in prostatectomy specimens in cabozantinib-treated patients versus controls.

Comprehensive Immune Profiling

We will focus on comprehensive immune profiling of available samples representing the cabozantinib-treated and untreated tumor microenvironment (TE) as well as baseline and longitudinal PBMC samples in cabozantinib-treated and untreated patients in an attempt to identify both: (1) baseline signatures that predict which patients might benefit from cabozantinib, as well as (2) pharmacodynamic signatures that could provide mechanistic insights regarding therapeutic responses. The TE (tissue) will be analyzed in the laboratory of [name] (Duke Chair of Pathology). The profiling platform to be used to analyze the peripheral blood (PBMC) samples will be highly standardized, polychromatic flow cytometry assays that have been developed by the Duke Immune Profiling Core (DIPC; Director: [name]) specifically for monitoring immune signatures in the context of immune checkpoint blockade trials.

Pathologic Response

Complete pathologic response (pCR) is defined as complete resolution of all cancerous glands in the prostatectomy specimen. Patients treated with cabozantinib who have pCR will be defined as *extraordinary responders*. Tissue from these patients' prostate biopsy will be collected for analysis and correlation with key correlative endpoints.

Relapse-free Survival

After completion of the treatment period (if applicable), prostatectomy, and safety follow up period (if applicable), patients will be followed for relapse-free survival, so that this rate may be estimated at 3 years (landmarked from the prostatectomy). *Relapse* is defined as biochemical recurrence (AUA guidelines), radiographic evidence of metastasis (in the opinion of the investigator), new treatment for prostate cancer or death. According to AUA guidelines, a biochemical recurrence is defined as a serum PSA ≥ 0.2 ng/mL, which is confirmed by a second determination with a PSA ≥ 0.2 ng/mL.

Apoptosis

TUNEL. Apoptotic index will be assessed in tissue biopsies and prostatectomy specimens from all patients using the TdT nick-end labeling technique.

Proliferation

Ki-67. Proliferation index (PI) will be assessed in tissue biopsies and prostatectomy specimens from all patients.

Angiogenesis

CD31. We will perform immunohistochemistry staining for CD31, an angiogenesis marker, in tissue biopsies and prostatectomy specimens from all patients on formalin-fixed tissue sections that are consecutive to those stained for apoptosis and proliferation.

HGF-c-MET Axis

c-MET. Tumor specimens will be evaluated for c-MET, HGF, and phospho-c-MET expression as a measure of pharmacodynamic response to cabozantinib treatment.

HGF/phospho-c-MET double stain. HGF is the ligand of the c-MET receptor and controls its activity through paracrine activation. HGF is secreted by prostate stromal cells and by inflammatory cells in the prostate stroma. HGF is also secreted by vascular smooth muscle cells. Stroma will be evaluated for expression of HGF as a measure of pharmacodynamic response to cabozantinib treatment.

Plasma Angiome

Blood for use in the plasma angiome multiplex ELISA will be collected as described previously.³⁰ Samples will be stored for possible future processing in the Phase I Biomarker Laboratory at Duke (Director: [name]), Molecular Reference Laboratory for the Alliance Oncology Cooperative Group, a national clinical trial research group sponsored by the National Cancer Institute.

Gene Expression Analysis

The Affymetrix® U133A 2.0 Microarray, or similar, will be used for all analyses. Microarray hybridization and scanning will be performed as previously described.³¹ A k-nn (nearest neighbor) analysis will be performed to identify genes that have their expression most closely associated with cabozantinib administration. Random permutation testing will be used to determine if the number of genes identified as having expression differences associated with cabozantinib administration is greater than would be expected by chance alone. Additional analyses can be performed to determine if particular patterns of gene expression are associated with response to cabozantinib. This analysis can initially be performed using pathologic response to cabozantinib as a dichotomous variable based on pre-established criteria. In this analysis, genes are identified in the control and cabozantinib-treated prostatectomy specimens that are most closely associated with response to cabozantinib using k-nn, similar to the analysis above. Using a similar dichotomous variable analysis, expression patterns will be correlated with VEGF and c-MET, HGF, and phospho-c-MET levels. Finally, we will test genes associated with apoptosis, androgen receptor signaling, c-MET activation,^{32,33} and a c-MET-specific endocytosis panel^{34,35} for correlation with response to cabozantinib. These studies will be performed and analyzed by [name] at the Duke Cancer Institute, Assistant Professor of Medicine and Research Scientist in the Genitourinary Oncology Laboratory. [name] completed a postdoctoral fellowship in the Duke Institute for Genome Sciences and Policy (IGSP) and has experience analyzing gene expression and pathway signatures in human solid tumors.

Mesenchymal Markers

An exploratory endpoint of this study will be to describe changes in mesenchymal markers associated with cabozantinib treatment. We hypothesize that patients treated with cabozantinib will have evidence of mesenchymal markers to a lower degree than controls, indicative of a mesenchymal-epithelial transition (MET).

Intratumoral Androgens

The importance of ongoing steroidogenesis within prostate tumors, despite anorchid serum androgen levels, is now appreciated.³⁶ Two recently reported studies of androgen suppression in the neoadjuvant-to-prostatectomy setting demonstrated that the androgen receptor (AR) axis is still active despite near

total ablation of tissue dihydrotestosterone (DHT) levels and impressive rates of pCR and near-pCR.^{37,38} Given the apparent inverse relationship between the AR and c-MET,³⁹ we hypothesize that patients treated with cabozantinib will have increased intratumoral androgen concentrations relative to the prostatectomy specimens of controls. In prostatectomy specimens, tissue androgen and androgen precursor levels (i.e. testosterone, DHT, DHEA, etc.) will be stored for possible analysis by mass spectrometry (MS) using methods previously described.⁴⁰ The same androgen levels in serum will also be measured at baseline and prior to prostatectomy.

Cell-free DNA (cfDNA)

We will collect double-spun platelet poor plasma EDTA samples for circulating cfDNA analysis. Samples will be stored at -80°C for later analysis in a non-CLIA format.

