Endpoints:	
Primary: Apoptotic index by cleaved caspase-3
 
Secondary: Description of immune biomarkers, including:
 
 • Immune phenotyping of paired peripheral blood and tumor tissue: Myeloid-derived suppressor cells (MDSCs), neutrophils, M1 macrophages, and M2 macrophages in tumor tissue • Immunohistochemical (IHC) analysis of CD8+, programmed death ligand-1 (PD-L1), cytotoxic T-lymphocyte-associated protein 4 (CTLA-4), interleukin-1 receptor antagonist (IL-1RA) and B7H3 in tumor tissue • Neutrophil chemotactic factors (CXCL12 and HMGB1) and MDSC-promoting cytokines (CCL5, CCL12, CD40) in tumor tissue 
Exploratory:
 
 1. Rates of pCR and \leqpT2 2. Relapse-free survival rate at 3 years 3. Quantification of TUNEL, Ki-67, and CD31 staining 4. Quantification of c-MET, VEGF, HGF, and activated c-MET in prostatectomy tissue 5. Correlation of vimentin, AR, SNAIL, AXL, and N-cadherin with cabozantinib exposure 6. Measurement of PTEN and p53 genomic and protein expression status in tumor tissue 7. Adverse events by CTCAE v5.0, dose intensity of cabozantinib 8. Blood loss at prostatectomy and duration of hospital stay 9. Angiome biomarkers 10. Gene expression patterns using RNA sequencing 11. Serum and intratumoral androgen concentrations 12. Alterations in cfDNA
Study Population:	Eligible patients will have histologic evidence of adenocarcinoma of the prostate and be deemed candidates for curative radical prostatectomy. They will have intermediate-or high-risk, clinically localized disease and have not received prior treatment for prostate cancer.
Phase:	Phase II
Description of Sites/Facilities Enrolling Participants:	This is a multicenter study of 30 evaluable subjects. Duke is the lead site for this trial. Subjects who do not receive 21 out of 28 days of planned study drug administration and proceed to radical prostatectomy within 14 (+3) days of their last dose of study drug (Arm A only) or do not proceed to radical prostatectomy (Arm B only) will be replaced. There will be a second site selected TBD.
Description of Study Intervention:	Patients will be assigned (Safety Lead-In Cohort) or randomized to either: (1) cabozantinib 40 mg PO daily for 4 weeks, followed by a 2 week drug

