5.2 EXCLUSION CRITERIA

Subjects cannot have the following:

1. Prior treatment for prostate cancer.
2. Major surgery or radiation therapy within 4 weeks of Day 1 on study.
3. Planned radiation therapy until at least 4 weeks after prostatectomy.

4. NCI CTCAE v5.0 grade 3 hemorrhage within 4 weeks of Day 1 on study.
5. Prothrombin time (PT)/INR or partial thromboplastin time (PTT) test $\geq 1.3 \times$ the laboratory ULN within 14 days before Day 1 on study (Arm A subjects only) or within 14 days of the completion of screening (Arm B subjects only)
6. Concomitant anticoagulation with oral anticoagulants (e.g., warfarin, direct thrombin and Factor Xa inhibitors) or platelet inhibitors (e.g., clopidogrel). However, low-dose aspirin for cardio protection is allowed (per local applicable guidelines).
7. History of or known metastatic prostate cancer.
8. QT_{cf} interval > 500 msec on baseline EKG.
9. The subject has uncontrolled, significant intercurrent or recent illness including, but not limited to, the following conditions:
 - a. Cardiovascular disorders:
 - i. Symptomatic congestive heart failure (CHF) New York Heart Association Class 3 or 4, unstable angina pectoris, ongoing cardiac dysrhythmias of NCI CTCAE grade ≥ 2 . coronary/peripheral artery bypass graft (CABG), within 6 months prior to screening.
 - ii. Stroke (including transient ischemic attack [TIA]), cerebrovascular accident (CVA), myocardial infarction (MI), or other ischemic event, or thromboembolic event (e.g., deep venous thrombosis, pulmonary embolism (PE)) within 6 months prior to screening.
 - b. Gastrointestinal (GI) disorders including those associated with a high risk of perforation or fistula formation:
 - i. Evidence of tumor invading the GI tract, active peptic ulcer disease, inflammatory bowel disease (e.g., Crohn's disease), diverticulitis, cholecystitis, symptomatic cholangitis or appendicitis, acute pancreatitis, acute obstruction of the pancreatic duct or common bile duct, or gastric outlet obstruction.
 - ii. Abdominal fistula, GI perforation, bowel obstruction, or intra-abdominal abscess within 6 months before first dose.
Note: Complete healing of an intra-abdominal abscess must be confirmed before first dose.
 - c. Clinically significant hematuria, hematemesis, or hemoptysis of > 0.5 teaspoon (2.5 ml) of red blood, or other history of significant bleeding (e.g., pulmonary hemorrhage) within 12 weeks before first dose.
 - d. Serious non-healing wound/ulcer/bone fracture.

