6.15 RELAPSE FREE SURVIVAL FOLLOW UP PERIOD

Arm A and Arm B subjects will be followed for relapse free survival for 3 years from date of prostatectomy. Follow up will occur every 3 months (+/- 1 month). Follow up may be obtained by a phone call, clinic visit or chart review.

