6.16 END OF STUDY

Reasons to discontinue the subject prior to 3 years include: biochemical progression, disease progression, new treatment for prostate cancer, withdrawal, or death. This determination may require obtaining outside records and interpretation by the investigator.

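### Adjuvant therapy started without recurrence counts as relapse and can end follow-up, so the exploratory 3-year relapse-free rate mixes recurrence with treatment decisions

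*Combined protocol and SAP*

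**What the plan says.** - **Endpoint.** The synopsis (1.1) lists "Relapse-free survival rate at 3 years" as an exploratory endpoint, and section 3 justifies it as a measure of efficacy.
- **Event definition.** Section 4.2, under relapse-free survival, counts four kinds of event: biochemical recurrence, then "radiographic evidence of metastasis (in the opinion of the investigator), new treatment for prostate cancer or death". For the first, "a biochemical recurrence is defined as a serum PSA ≥ 0.2 ng/mL", with a second confirming value. No condition is attached to new treatment, and the term is not defined.
- **Follow-up.** Section 6.15: "Arm A and Arm B subjects will be followed for relapse free survival for 3 years from date of prostatectomy". Contact is every 3 months by phone, visit or chart review.
- **End of follow-up.** Section 6.16: "Reasons to discontinue the subject prior to 3 years include: biochemical progression, disease progression, new treatment for prostate cancer, withdrawal, or death".
- **Entry.** Section 5.2 excludes men with "Prior treatment for prostate cancer" and, in exclusion 3, "Planned radiation therapy until at least 4 weeks after prostatectomy".
- **Other restrictions.** The ban on non-protocol systemic anticancer treatment in section 8.1 applies to the 28 days of dosing in Arm A.
- **Analysis.** Section 11.1 gives no rule for relapse-free survival: no censoring rule, no handling of adjuvant therapy and no sensitivity analysis.

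**The concern.** The population is intermediate- to high-risk, so some men may be offered adjuvant therapy after surgery with no detectable recurrence. Under the definition, such a man has relapsed on the day treatment starts. Under 6.16 he may then leave follow-up, so whether he later had a confirmed PSA rise or metastasis need not be recorded.

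The decision to give adjuvant therapy is made open-label, with the surgical pathology in hand. Pathologic stage is itself an exploratory endpoint that the drug might change. If adjuvant use differs between arms, for either reason, the difference will look like a difference in relapse. Because the reason for treatment need not be recorded and follow-up may stop, the analyst cannot fully separate the two afterwards.

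**Working it through.** **Plan's own figures.** The documents state no figure for relapse-free survival. The numerical claims in section 11.1 concern the primary t-test. With 10 and 20 patients, two-sided 0.05 and 28 degrees of freedom, the noncentral t gives 70.3% power at 1.0 SD and 96.2% at 1.5 SD, against the stated 70% and 96%. These stand, and nothing below touches them.

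**Following one man through the text.**
1. Radiation planned for week 4 or later after surgery does not exclude him (5.2, exclusion 3). No other section bars adjuvant therapy after surgery in either arm.
2. He starts adjuvant therapy with no recurrence. Section 4.2 scores an event.
3. Section 6.16 lists that event as a reason to discontinue him. Later PSA and metastasis status need not be collected.
4. Section 11.1 contains nothing that reclassifies or censors him.

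**Inputs for size.** From section 11.1: 20 men in Arm A, 10 in Arm B. Assumed, because the documents give neither:
- S, the true 3-year rate when adjuvant therapy is not counted: 0.50 to 0.80.
- a, the share of men starting adjuvant therapy before any other event: 0.05 to 0.30.

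Men given adjuvant therapy are taken to have the same S as the rest.

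**One man.** 1/20 = 5 points in Arm A and 1/10 = 10 points in Arm B. These are upper limits, since he might have relapsed within 3 years anyway.

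**Whole arm.** Rate as defined = (1 - a) × S, so the gap is a × S.

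| a | Rate as defined, S = 0.70 | Gap (points) |
|---|---|---|
| 0.05 | 0.665 | 3.5 |
| 0.10 | 0.63 | 7 |
| 0.20 | 0.56 | 14 |
| 0.30 | 0.49 | 21 |

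Over the assumed ranges the smallest gap is 0.05 × 0.50 = 2.5 points and the largest is 0.30 × 0.80 = 24 points. If the men given adjuvant therapy have a lower S than the rest, the gap is smaller.

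**Unequal use.** With S = 0.70 in both arms and a = 0.10 in one and 0.30 in the other, the apparent difference is (0.30 - 0.10) × 0.70 = 14 points with no difference in recurrence.

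**Precision for scale.** At a rate of 0.70 in both arms, the standard error of a difference is √(0.21/20 + 0.21/10) = √0.0315 = 0.177. The 95% half-width is 1.96 × 0.177, about 35 points.

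**The case against.** Counting any new treatment as an event is a recognised composite strategy, and no section says the endpoint is meant to isolate recurrence. That stands: the definition is not an error. Replacing it with one that depends on the investigator's stated reason would create a different problem. A man treated for a PSA rise still below 0.2 ng/mL, or before the confirming value, could be scored relapse-free, and the stated reason is itself an open-label judgement. This is why the composite should be kept.

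The size should also be discounted. The endpoint is exploratory and unpowered, the objective is to describe each arm, section 11.1 plans no between-arm test of it, and 6 of the 20 Arm A men are not randomized. A 14-point artefact lies well inside a half-width of about 35 points.

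A reader might infer that planned adjuvant radiation is definitely scored as relapse. The documents do not go that far. That such radiation is allowed follows from what exclusion 3 leaves out; no section plans or expressly permits it. Because new treatment is undefined, a site could decide that therapy planned before entry is not new. Radiation chosen later because of adverse pathology is a separate case that does not depend on exclusion 3. The ambiguity is a reason to clarify, since two sites could score identical men differently.

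**Conclusion.** The point holds as a limited, inexpensive improvement to one exploratory endpoint. As written, adjuvant therapy without recurrence is scored as relapse, and follow-up may end there. Under the assumed rates (S of 50-80%, adjuvant use of 5-30%, the same S in men given adjuvant therapy), the reported 3-year rate is 2.5 to 24 points below one that does not count adjuvant therapy. The real adjuvant rate is unknown from the documents, and the gap is zero if no man receives it.

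A reader might infer that true recurrence is never observed, or that the information cannot be recovered at all. Neither is supported. Only men who start such therapy before any other event are affected; in everyone else, confirmed PSA recurrence, metastasis and death are still captured. Charts may show why treatment began, and section 6.16 itself foresees obtaining outside records, so censoring at treatment start would often be possible. What may be lost is the course after that treatment. The primary endpoint, sample size and safety rules are not affected.

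**What to change.** - **Section 4.2.** Keep the any-new-treatment composite. State whether therapy planned before entry counts as new.
- **CRF.** Add a field for the date and reason for new treatment: adjuvant or planned without recurrence, or started for a PSA rise or radiographic recurrence.
- **Section 6.16.** Do not end follow-up for new treatment started without recurrence. Continue the existing 3-monthly phone, visit or chart-review follow-up of PSA and metastasis status to 3 years.
- **Section 11.1.** Report a second estimate beside the composite, in which the events are biochemical recurrence, metastasis, treatment started for a rising PSA or recurrence, and death. Including treatment for a rising PSA covers men treated below 0.2 ng/mL or before confirmation.

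The cost is a few lines of wording, one CRF field and some extra chart review. The second estimate must be read knowing that adjuvant therapy may delay recurrence and that the reason for treatment is the investigator's judgement. The change concerns scoring and data collection only, not whether or when any treatment is given.

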Exploratory Objectives:	
 1. To estimate the pathologic complete response rate (pCR) and \leqpathologic T2 (\leqpT2) rate in each arm. 2. To evaluate relapse-free survival in each arm. 3. To compare apoptosis (TUNEL), proliferation (Ki-67), and microvessel density (CD31) indices in prostatectomy specimens from patients who undergo immediate prostatectomy versus those treated with cabozantinib prior to prostatectomy. 4. To measure expression levels of c-MET, VEGF, and HGF, as well as activation status of c-MET in prostate tissue. 5. To describe changes in plasticity signaling markers associated with prostate tumors, including vimentin, AR, SNAIL, AXL, and N-cadherin with cabozantinib exposure. 6. To evaluate PTEN and p53 genomic and protein expression status in tumor tissue 7. To demonstrate that cabozantinib is safe and tolerable in patients undergoing radical prostatectomy. 8. To demonstrate that surgery is safe and feasible in patients undergoing treatment with cabozantinib. 9. To collect plasma angiome samples (multiplex ELISA) for analysis and correlation with primary and key secondary endpoints. 10. To describe gene expression patterns (in particular those associated with apoptosis, androgen receptor signaling, c-MET activation, and a c-MET-specific endocytosis panel) correlated with cabozantinib administration using RNA sequencing.

	
 11. To explore changes in serum and intratumoral androgen concentrations related to cabozantinib treatment. 12. To collect cell-free DNA (cfDNA) for analysis and correlation with primary and key secondary endpoints.

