Sample Size Justification. The primary endpoint of this randomized phase II study is the apoptotic index by cleaved caspase-3 in prostatectomy specimens following 4 weeks of treatment with cabozantinib compared with prostatectomy specimens of untreated patients. The target sample size of convenience is 30 patients where the randomization allocation ratio will be 2:1 cabozantinib-to-control. The randomization will not be stratified on any variable. The null hypothesis is that the mean apoptotic indices are equal between the two groups. The percent of tumor cells positive for cleaved caspase 3 staining for each patient will be evaluated for the primary objective. The 6 subjects assigned during the Safety Lead-In Cohort are included in the 30 patient sample size and 2:1 randomization allocation ratio.

Based on data from a prior, unpublished pre-prostatectomy study of sunitinib, we expect the controls to have minimal staining (i.e., $\leq 5\%$). In the proposed study we will enroll 10 controls and 20 cabozantinib-treated patients to demonstrate increased staining (i.e., $>5\%$). A two sample t-test will be used to compare group means. With 10 and 20 evaluable patients in the control and cabozantinib-treated groups, respectively, the test will provide 70% power to detect a mean (for positive tumor cells percentage) difference of one-fold standard deviation based on a two-sided type I error of 0.05; or 96% power to detect an one-and-half fold standard deviation difference. Assuming a 10% unevaluable rate, we will enroll up to 33 patients total to have 30 evaluable patients.

Data Analysis. Box plots and statistical summaries of apoptotic (cleaved caspase-3, TUNEL), proliferation (Ki-67), and MVD (CD31) indices will be presented. In addition, the t-test will be used to compare the two arms on apoptotic index, proliferation and MVD indices. Further, the Chi-square test will be used to compare the two treatment arms on pathologic complete response rate (pCR) and pathologic T2 (pT2) rate. The angiome, gene expression, cell-free DNA and mesenchymal markers analyses will be reported descriptively as the trial's limited sample size will not permit definitive analyses for these exploratory objectives. The t-test will be used to compare the two arms' serum and tissue androgen and androgen precursor levels.

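### The gene-list test in Section 4.2 asks only whether more genes differ than chance predicts; it does not limit or report the false share of the list, which per-gene q-values would do at little cost

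*Combined protocol and SAP*

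**What the plan says.** Section 4.2 (Gene Expression Analysis) sets out two steps. The first is selection: "A k-nn (nearest neighbor) analysis will be performed to identify genes that have their expression most closely associated with cabozantinib administration". The second is a label-permutation test on the size of the resulting list: "Random permutation testing will be used to determine if the number of genes identified as having expression differences associated with cabozantinib administration is greater" than chance alone would give. The section gives no number of neighbours, gene-level cut-off, list size, FDR, q-value or family-wise error rate. It ends by planning to test four gene groups (apoptosis, androgen receptor signaling, c-MET activation, c-MET endocytosis) against response to cabozantinib.

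Exploratory objective 10 (Sections 1.1 and 3) asks for gene expression patterns, in particular in those same four groups, "correlated with cabozantinib administration using RNA sequencing". Section 4.2 names a different platform: "Microarray, or similar, will be used for all analyses".

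Section 11.1 adds no gene-level method. It says that "gene expression, cell-free DNA and mesenchymal markers analyses will be reported descriptively as the trial's limited sample size" does not allow definitive analysis. Section 4.2 also opens with "Please see the lab manual for further details of these analyses"; that manual is not among the documents reviewed.

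**The concern.** The permutation test addresses a single null hypothesis, that no gene differs between arms. Objective 10 asks which patterns differ. Rejecting the global null is compatible with a list that is nearly all real or mostly noise, and a reader told only that the count exceeds chance cannot tell which. Section 2.2 describes the study as hypothesis-generating, and a hypothesis-generating list is most useful when its expected false share is known.

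There is a secondary issue of power. When genes move together, the permuted count varies more from one permutation to the next, so a larger observed count is needed for significance. The test keeps its type I error but can become insensitive.

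**Working it through.** **Inputs from the documents.** Section 11.1: "With 10 and 20 evaluable patients in the control and cabozantinib-treated groups, respectively", so 10 v 20 and 28 degrees of freedom. The plan gives no figure for the gene analysis. As a check on the calculation, its stated power for the primary endpoint (70% at 1 SD and 96% at 1.5 SD, two-sided 0.05) reproduces with the noncentral t as 70.3% and 96.2%.

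**Assumptions not in the documents.** 5,000 genes, of which 50 truly change by 1.5 or 2 SD. Genes are selected by a two-sided t-test at p<0.01 or p<0.001, standing in for the unstated nearest-neighbour cut-off.

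**Step 1: false share of the list.** The noncentrality is δ × √(10 × 20 / 30) = 2.582δ. Per-gene power is the probability that |T| exceeds the two-sided critical value on 28 df. Expected false genes = (5,000 − 50) × α. Expected true genes = 50 × power. False share ≈ false / (false + true).

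| Cut-off | Shift | Power per gene | False genes | True genes | False share |
|---|---|---|---|---|---|
| 0.01 | 1.5 SD | 0.857 | 49.5 | 42.8 | 49.5/92.3 = 54% |
| 0.01 | 2 SD | 0.989 | 49.5 | 49.4 | 49.5/98.9 = 50% |
| 0.001 | 1.5 SD | 0.583 | 4.95 | 29.2 | 4.95/34.1 = 15% |
| 0.001 | 2 SD | 0.914 | 4.95 | 45.7 | 4.95/50.7 = 10% |

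Simulation of the same settings agrees. With independent genes at p<0.01 the count test was significant every time, with about half the list false. At p<0.001 it was significant every time, with about 8-16% false.

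**Step 2: range over other assumptions.** With 10,000 genes, 50 changed by 1.5 SD and p<0.01, the share is 99.5/(99.5 + 42.8) = 70%. With 500 changed and p<0.001 it is 9.5/(9.5 + 291.6) = 3%. Across simulated scenarios of this size, including correlated genes, a significant count test accompanied lists averaging from about 3% to 83% false.

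**Step 3: power of the count test under correlation.**
- 5,000 genes, 50 changed, p<0.01, shared factors explaining 30-50% of each gene's variance: mostly about 20-35%. Some runs at 50% shared variance gave 12-18%.
- 10,000 genes, 50 changed by 1.5 SD, p<0.01: 100% if independent, 33% in correlated blocks of 100 and 8% in blocks of 500 (within-block correlation 0.5). The 95th percentile of the permuted count rises from about 116 (independent) to about 220 (blocks of 500).
- Same model at p<0.001: 100%, 100% and 72%. With 500 changed genes: 100% throughout.
- With no true change the test rejected in 1-9% of 100 trials per setting, consistent with 5%.

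**Step 4: what an FDR method gives on such data.** With 5,000 genes, Benjamini-Hochberg at 10% gave about 8-12% false and found about 25 of the 50 true genes at 1.5 SD or 45-46 at 2 SD. With 10,000 genes, Benjamini-Hochberg at 5% gave a realised FDR of 3.7-5.6% in every scenario with true changes, correlated or not.

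**Step 5: the panels.** Objective 10 relates the four gene groups to cabozantinib administration. Section 4.2 tests them against response to cabozantinib. The comparison by arm that the objective asks for is not stated for these groups.

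**The case against.** The strongest reply has four parts.

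First, the size of the problem depends on a cut-off that the plan does not give. This stands: at p<0.001 the false share is modest and the loss of power nearly disappears. A reader might infer that the list must be largely false, or that the test necessarily misses real changes when genes are correlated. The documents support neither; both depend on the cut-off, the number of changed genes and the correlation structure.

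Second, a reader might infer that a non-significant count test would cause real genes to be discarded, or that a significant one sends the whole list forward as the basis for choosing combination partners. Section 4.2 never makes the list conditional on the test, and no section gives this list that role. Section 11.1 has it reported descriptively, and Section 3 justifies objective 10 as collecting samples for possible later analysis. This stands and lowers the consequence. It does not remove the point, because Section 4.2 still plans a formal test that answers a different question from the objective.

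Third, the planned permutations already hold the missing quantity: the mean permuted count divided by the observed count estimates the false share. In simulation at p<0.01 this ratio was 0.50-0.58 against a true share of 0.46-0.54. This stands too, but the plan does not say the ratio will be computed or reported. It makes the remedy easier.

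Fourth, the lab manual may contain more. The finding is therefore limited to the reviewed documents.

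**Conclusion.** The point holds in a limited form. In the reviewed documents, the only error control for the cabozantinib gene list is a valid global test that says nothing about the false share of the list. Under the 5,000-gene assumptions, a significant result is compatible with about half the list being false at p<0.01 or about 8-16% at p<0.001. At p<0.01, correlation can reduce the test's power to about 20-35%.

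These figures rest on assumed gene numbers, effect sizes, correlation and a t-test stand-in for the unstated selection rule. Monte Carlo error is up to about 5 points in the 10,000-gene runs. Permuting labels also assumes that the two arms are exchangeable under the null, although 6 of the 20 treated patients are assigned and not randomized (Section 11.1).

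Because the analysis is exploratory and descriptive and the test is not stated to gate the list, this is an improvement worth making and not a serious error.

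**What to change.** In Section 4.2:

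1. Name a per-gene two-arm statistic suited to the platform actually used (a moderated t for array data, a count model for sequencing), and reconcile the platform with objective 10.
2. Report an FDR q-value for each listed gene, from Benjamini-Hochberg or from the permutations already planned, with a stated threshold such as 10%.
3. Keep the count test only as a global check.
4. Test the four named panels by arm as pre-specified gene sets, in addition to the planned comparison with response.

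Q-values are compatible with descriptive reporting, so Section 11.1 needs only a cross-reference. The cost is protocol wording and standard software, with no new samples or patients. The drawback is that the reported list may be shorter.
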